## Home Based Virtual Rehabilitation for upper extremity

**Title of Project:**

**Principal Investigator:**

**[name] PT PhD**

**Funding Source(s):**

**NIDILRR #90RE5021-01-00**

**NIH NICHD #1R15HD095403-01A1**

### 1. Purpose/Specific Aims

The overarching aim of this study is to provide a mechanism for patients to engage in progressive motor practice for a meaningful time period. We aim to improve on the positive outcomes found in our work on patients in the chronic phase and the pilot work being done on patients in the acute in-patient phase post stroke to determine whether we can further improve functional recovery using a home based system.

Aim 1: Evaluate compliance with Home-Based Virtually Simulated hand/arm gaming activities and two computer game groups, one with motivation enhanced (ME) simulations and one with non-enhanced (MnE) versions, as compared to compliance with Standard hand/arm home Exercises (HBSE). Hypothesis: Participants in the ME and MnE group will show significant compliance as compared to the control group (HBSE) and the ME group will be superior to the MnE group.

Primary Outcome Measures: For the HBVS group, 1) time on task will be measured by the daily computer file time stamp and 2) amount of moving time will be measured by the actual movement time recorded by the games. For the computer games groups 1) time on task will be measured by recording start and stop time of practice in a notebook and 2) amount of moving time will be measured by commercially available activity monitors.

Aim 2: Evaluate the effectiveness of home-based virtually simulated hand/arm gaming activities (HBVS) for individuals with stroke as compared to a program of standard hand/arm home exercises (HBSE). Hypothesis: Participants completing HBVS training will exhibit significantly improved clinical, kinematic and neurophysiological outcomes as compared to the control group (HBSE).

Primary Outcome Measures for Aim 2: Wolf Motor Function Test, Upper Extremity Fugl-Meyer Assessment of Sensorimotor Recovery after Stroke, Action Research Arm Test, Perception of System Questionnaire, the Stroke Impact Scale, Kinematics, Cortical mapping.

Aim 3: Evaluate the impact of the motivation enhancements designed into computer games to provide a more enjoyable training experience. Hypothesis: Enjoyment of the games will be a more valid predictor of compliance than personal factors.

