### ***3.1. Duration of Study***

Each subject will perform a pre-study evaluation, train using one of the protocols for three to twelve months, perform a post study evaluation as well as one and six month retention evaluations.

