### ***3.3 Sample Size Justification***

In this pilot study we will seek sufficient power to detect a clinically significant difference in the Wolf score changes in these two pre-planned, primary comparisons. To evaluate these effects of training, we will assume a power level of .8 and a significance level of 0.05. With presumed correlation among repeated measures of 0.1 and effect size of 0.3, we will need a sample size of 25 subjects in each of the three groups (HBVS, ME and MnE) to observe a significant effect for the first comparison (G\*Power, version 3.1.5). Although we will screen for patients with homogeneous impairments, by its nature stroke is an extremely variable condition. Due to possible subject attrition, we will use a total of 30 subjects in each of the two groups.

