### **4.2 Dependent Variables or Outcome Measures**

All subjects will come to our lab and complete a quality of life questionnaire (Stroke Impact Scale) [4] and undergo clinical and kinematic testing immediately pre and post training as well as at 1 and 6 months post training. Additionally they will complete a perception of the system questionnaire [5] after training is completed.

Clinical Measures. The main clinical outcome will be the Wolf Motor Function Test [6] because it is a balanced test of arm and hand use [7, 8]. The secondary measures will be the Upper Extremity Fugl-Meyer Assessment[9], the Action Research Arm test[10], and Kinematic/Kinetic Measures. To explore the mechanism of improvement, changes in kinematics and kinetics of the hand and arm will be used to elucidate recovery of impairment. Two types of kinematic data will be collected; 1) data obtained from the patient's daily performance during the training and 2) data collected during the 4 testing

periods. Data obtained from the patient's daily gaming performance during the training will include duration of motor activity, hand opening and closing range of motion, pronation and supination range of motion, maximum fractionation (a measure of finger individuation), hand opening velocity, hand trajectory smoothness, game duration and game score.

Data collected during the 4 testing periods includes computer-based outcome measures and the Real-World Reach to Grasp Test. There are four computer based outcome measures in this data set. 1) Maximum Finger Opening is collected using a CyberGlove™ (Immersion, USA) (2) Pinch Force Tracking Error measures the ability to control active finger extension and flexion to modulate their pinch grip force to control a cursor to track a sine wave. (3) Maximum Pinch Force is measured as the maximum force a subject can exert on a force sensor held between their paretic thumb and index finger and, (4) Figure 8 Tracking Error measures forearm and shoulder control needed to trace a horizontal figure 8 shape while the arm is in a supported horizontal position[11] (5) Max finger extension and abduction (collected using a CyberGlove) (6)Maximum supination with hand open, measured with an Optitrack system. (7) Maximum pronation with hand open, measured with an Optitrack system (8) Maximum MCP flexion with PIP and DIP extension measured with an Optitrack system.

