### **5. Data Handling and Statistical Analysis**

All efforts will be made to keep subjects' personal information confidential. All subject names will be removed from the data and the data will be tagged using a coded ID number.

Demographic, clinical outcome and survey data will first be recorded on paper. All kinematic and computerized performance data will be collected on computer. These computer files will be identified by the coded subject ID number. All data will be transferred to an Excel spreadsheet with subjects identified by this same ID number. Spreadsheets will be stored on a drive that is password protected. Data will only be accessible to study staff and will be retained for seven years. The link between subject identity and subject ID number will be destroyed when data collection is completed.

Our primary outcome measures will be the WMFT (Aim 2) and the duration of motor activity (measure of compliance, Aim 1). The primary outcome measures and all secondary outcome measures described above will be subjected to a repeated measured analysis of variance, with between-group factors Therapy Type (Virtual Simulations (VS), Standard Exercise (SE)) and within-group factor Test (Before, Post, One Month retention, Six Months Retention). Our post-hoc analyses of the Therapy Type by Test interaction effects will focus on the Month 1 versus Month 6 comparison. We will be quantifying training effects by comparing group means as well as by percent change in performance, and by comparing the recovery curves obtained from Tests 1-4. All clinical outcomes used are well established measures of upper extremity functional recovery with published minimum clinically important differences which we will use to evaluate the significance of our findings.

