**Outcomes Measures:** (See Table 4 for a summary of all measures and Figure 6 for a data collection Schedule). The impact of game mechanics on motivation to perform the simulation that is specifically related to

the experience of using the simulation not the general motivation to improve their hand function or increase their independence, etc. will be measured utilizing the Intrinsic Motivation Inventory (IMI) (58). IMI data will be measured following the first training session (Collection 2) to measure the subjects' initial reaction to the system and simulations as well as after the twelfth session (Collection 3) and after the final training session (Collection 4) to chart subjects' responses to repeated use.

*Statistical Analysis:* (See Table 5 for a summary of all planned comparisons) Our primary outcome measures will compare differences in IMI scores after the initial exposure to the training program. Data will be evaluated for normality and transformed if necessary for evaluation. Baseline group equivalence will be evaluated via t-test. The within-and-between group interaction will be examined to evaluate differences in change between groups.

**Aim 2: To test the impact of intrinsic motivation on adherence to a telerehabilitation exercise program in persons with strokes.**

**Table 4** Outcome measures

Motivation Measure	
Intrinsic Motivation Inventory	Measurement of emotional response to an activity.
Adherence Measures	
Number of interventions days	Recorded by system
Total intervention time	Recorded by system
Average intervention day time	Recorded by system
Clinical Measures	
Upper Extremity Fugl-Meyer Assessment (66)	A 33 item battery which evaluates reflexes, movement patterns in and out of synergy, grasp, and coordination (impairment level)
Action Research Arm Test (62)	19 item battery which tests the ability to handle items of different size, shape and weight (activity level)
Box and Blocks Test (67)	Standardized dexterity test with well-established benchmarks for persons with CVA and age-matched healthy populations
Quality of Life Measure	
Stroke Impact Scale (69)	Patient reported assessment of multiple activity and participation level domains post stroke including hand function, activities of daily living and social participation.
Kinematic/Kinetic Measures	

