these steps: 1) A trained interviewer will ask open-ended questions in telephone interviews, allowing participants to reflect on and describe their experiences. 2) Investigators will read participants' narratives to develop a general sense of the subjects' experiences and attitudes toward the rehabilitation program. 3) Investigators will identify emerging narrative themes in participants' experiences and attitudes toward the program. 4) Finally, an iterative coding process will be used to refine initial findings and synthesize these themes.

*Statistical Analysis:* (See Table 5 for a summary of all planned comparisons.) Linear regression will be used to evaluate the effects of IMI (From Data Collection 1) on total time (Collected during training sessions).

**Aim 3: To test the impact of motivation enhanced, game-based interventions on the effectiveness of a telerehabilitation exercise program in persons with strokes.**

*Rationale:* Studies of clinic based interventions targeting hand function in persons with stroke have produced measurable changes in hand function that do not substantially reduce hand related disability. Study of a long term, home based program emphasizing adherence will inform the development of sustainable alternatives to costly clinic based interventions that fall short of the ultimate goal of rehabilitation.

*Hypothesis:* We predict that subjects in the ME group will demonstrate larger improvements in hand function as measured by the Action Research Arm Test (ARAT) than those performing UC interventions. We further predict that subjects in the ME group will demonstrate larger reductions in impairment and larger improvements in measures of motor control and quality of life than UC group subjects.

*Subjects:* The same subjects will be utilized for Aims 1-3.

*Outcome Measures:* (Please see Table 4 for the full listing and description of the proposed clinical and quality of life measures.) A trained RA, blinded to group assignment will collect all outcome measures described in Table 4 immediately prior to training, immediately after training and 3 months after training (Data Collections 1 and 2). The RA will be blinded to previous test scores during post testing and retention testing.

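### The only named follow-up of the Therapy Type by Test interaction, Month 1 versus Month 6, compares two post-training tests, so it measures retention and not the improvement from Before that Aim 2 predicts

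*Protocol*

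**What the plan says.** Protocol section 5 makes the WMFT the primary outcome for Aim 2. It analyses the WMFT by repeated-measures ANOVA with Therapy Type (virtual simulations, VS; standard exercise, SE) between groups and Test (Before, Post, one-month and six-month retention) within groups. The follow-up is then stated: "Our post-hoc analyses of the Therapy Type by Test interaction effects will focus on the Month 1 versus Month 6 comparison".

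Other places that bear on this:

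- **Timing.** Protocol section 3.1 has each subject, after training, "perform a post study evaluation as well as one and six month retention evaluations". Section 4.2 schedules testing "immediately pre and post training as well as at 1 and 6 months post training".
- **Hypothesis.** Protocol section 1, Aim 2: "Participants completing HBVS training will exhibit significantly improved clinical, kinematic and neurophysiological outcomes as compared to the control group (HBSE").
- **Sample size.** Protocol section 3.3 seeks "sufficient power to detect a clinically significant difference in the Wolf score changes in these two pre-planned, primary comparisons". It names no time points for those comparisons.
- **Other summaries.** Section 5 also speaks of "quantifying training effects by comparing group means as well as by percent change in performance" and of comparing recovery curves over the four tests. No pair of tests and no significance test is attached to these.
- **SAP.** Under Aim 1 the SAP points the reader to a table ("See Table 5 for a summary of all planned comparisons") that is not in the supplied text. The SAP that can be read compares motivation-enhanced with un-enhanced games. Its Aim 3 hypothesis on hand function uses the Action Research Arm Test, so it does not supply a VS versus SE contrast on the WMFT.

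**The concern.** The omnibus interaction has 3 degrees of freedom and tests whether the arms change differently anywhere across the four tests. Saying where they differ is the job of the follow-up, and the plan directs that follow-up to a pair without the Before test. Such a pair cannot measure gain from training.

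Two errors of interpretation follow:

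- **A real, lasting benefit looks absent.** If one arm gains more and keeps the gain, the Month 1 to Month 6 changes are equal in the two arms. A significant omnibus result would then usually be followed by a non-significant named contrast. On the supplied text, the contrast that answers Aim 2 would have to be picked after the data are seen.
- **Later decline looks like benefit.** If both arms gain equally and one then loses ground, the named contrast can be significant. That is a genuine retention difference, but it does not show that one arm gained more from training.

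**Working it through.** **The plan's own figure.** Section 3.3 gives 25 per group for power 0.8, alpha 0.05, correlation 0.1 and effect size 0.3 (read as Cohen's f). This reproduces for the between-groups main effect with 2 groups and 2 tests: noncentrality N·m·f²/[1+(m−1)ρ] = 50·2·0.09/1.1 = 8.18 on F(1, 48), power 0.800. The interaction variants with 2 groups need 21, 17 or 15 per group for 2, 3 or 4 tests. The stated 25 therefore does not describe the power of the named contrast.

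**Inputs.** From the plan: 25 per arm, alpha 0.05, correlation 0.1, four tests. Assumed: two-sided testing, equal correlation between all tests, correlations of 0.5 and 0.8 as well as 0.1, and the benefit sizes. Let δ be the between-arm difference at (Before, Post, Month 1, Month 6) in SD units. A benefit d that is gained and fully kept is δ = (0, d, d, d).

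**Formulas, with d = 0.6 and ρ = 0.1**

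1. *Month 1 versus Month 6.* The expected value is δ(Month 6) − δ(Month 1) = 0.6 − 0.6 = 0. The rejection rate is 0.05 for any d, ρ or sample size.
2. *Omnibus interaction.* The mean of δ is 0.45, and Σ(δ − mean)² = 0.45² + 3·0.15² = 0.27. Noncentrality is [n₁n₂/(n₁+n₂)]·0.27/(1−ρ) = 12.5·0.27/0.9 = 3.75 on F(3, 144). Power is 0.329.
3. *Post adjusted for Before.* The variance is 1 − ρ² = 0.99, and the standard error is √(0.99·2/25) = 0.281. Noncentrality is 0.6/0.281 = 2.13 on 47 df. Power is 0.551.
4. *Unadjusted Before-to-Post change.* The variance is 2(1−ρ) = 1.8, and the standard error is √(1.8·2/25) = 0.379. Noncentrality is 1.58 on 48 df. Power is 0.341.

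**Benefit of 0.6 SD fully kept, 25 per arm**

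| Test | ρ = 0.1 | ρ = 0.5 | ρ = 0.8 |
|---|---|---|---|
| Month 1 versus Month 6 | 0.050 | 0.050 | 0.050 |
| Omnibus interaction | 0.329 | 0.560 | 0.940 |
| Post adjusted for Before | 0.551 | 0.670 | 0.934 |
| Unadjusted Before-to-Post change | 0.341 | 0.547 | 0.908 |

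**After a significant omnibus result** (simulation, 6,000 trials per setting, d = 0.6): Month 1 versus Month 6 is significant in 12% / 8% / 5% of those trials, and adjusted Post in 66% / 80% / 95%. At d = 1.2 and ρ = 0.1 the figures are 5% and 99%.

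**Other benefit sizes at ρ = 0.1** (Month 1 versus Month 6 / omnibus / adjusted Post):

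- 0.3 SD: 0.050 / 0.109 / 0.181
- 1.2 SD: 0.050 / 0.909 / 0.987
- 1.39 SD: 0.050 / 0.972 / 0.998. For this pattern the interaction effect is f = d·√3/8, so 1.39 SD corresponds to f = 0.30.

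**If VS pools both game groups** (50 versus 25, d = 0.6): Month 1 versus Month 6 stays at 0.050. The omnibus has 0.433 / 0.703 / 0.985 and adjusted Post 0.680 / 0.797 / 0.981.

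**Patterns other than full retention**

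- Equal gain, then one arm loses 0.6 SD between Month 1 and Month 6, δ = (0, 0, 0, −0.6): the named contrast is significant in 0.341 / 0.547 / 0.908, adjusted Post in 0.050.
- Half of a 0.6 SD benefit lost by Month 6: the named contrast has power 0.121 / 0.180 / 0.376.

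**The case against.** The strongest reply is that the sentence is secondary. The main analysis is the ANOVA over all four tests, which includes Before. The Month 1 versus Month 6 work is labelled post hoc, and nothing says that it decides Aim 2 or rules out other follow-ups. The next sentence turns to training effects through means, percent change and recovery curves, and section 5 goes on to invoke published minimum clinically important differences. An interest in retention also fits section 2, which argues that sustained training matters for keeping function as well as gaining it.

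Much of this stands. The omnibus test is valid, the summaries can show change from Before, and retention deserves a contrast. But no pair or test is attached to those summaries. Section 3.3 claims pre-planned comparisons without time points. The one pair that the Protocol does name leaves out Before. Table 5 of the SAP cannot be checked; whatever it holds, the Protocol sentence would still point elsewhere.

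A second objection is that comparing the plan with adjusted Post changes both the time points and the method. This is right. Changing only the time points, to unadjusted Before-to-Post change, gives 34% / 55% / 91%, about the same as the omnibus at 33% / 56% / 94%. The extra power at low correlation comes from adjusting for Before. That adjustment costs nothing, but the case for changing the contrast rests on what it measures, not on power.

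**Conclusion.** The point holds and should be fixed. The only time-point pair named for following up the interaction cannot show the improvement that Aim 2 predicts. For a fully kept benefit its rejection rate is 5%; this depends on no assumed benefit size, correlation or sample size. The other percentages rest on the assumed benefit sizes and on equal correlation between tests. The omnibus interaction is unaffected, so the defect lies in the interpretation of a significant result and not in the validity of the main test. Section 5 does not define Month 1 and Month 6 word for word. The factor levels listed just before, with sections 3.1 and 4.2, leave the two retention tests as the natural reading.

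**What to change.** In Protocol section 5, replace Month 1 versus Month 6 as the focus of the interaction follow-up with one pre-specified between-arm WMFT contrast that includes Before:

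- **Primary:** preferably the VS minus SE difference at Post, adjusted for the Before score.
- **Secondary:** the same adjusted difference at six months. The sponsor may make this one primary instead, if that is stated before the data are seen.
- **Secondary, retention:** Month 1 versus Month 6, labelled as such.

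The cost is a few sentences. All four tests are already scheduled, so no visits, measures or patients are added. The drawback is that one primary time point is fixed: with Post as primary, a benefit that appears only later would be seen only in the secondary contrasts. At correlation 0.8, adjusted Post has about the same power as the omnibus (93% and 94% at 0.6 SD), so the gain there is knowing which tests differ.

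### Protocol Section 5 names no baseline-adjusted estimate; at the plan's assumed correlation of 0.1, unadjusted change and percent change have much less power than an adjusted difference

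*Protocol*

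**What the plan says.** Protocol Section 5 names the Wolf Motor Function Test (WMFT, Aim 2) and duration of motor activity (Aim 1) as primary. It states that primary and secondary outcomes "will be subjected to a repeated measured analysis of variance", with Therapy Type (two levels) between subjects and Test (Before, Post, one month, six months) within subjects. It then says: "We will be quantifying training effects by comparing group means as well as by percent change in performance", and adds a comparison of recovery curves over the four tests. Published minimum clinically important differences are the stated yardstick for the clinical outcomes.

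Section 5 does not define the reference score for percent change, although Before is the natural one. It does not say whether percent change is tested, and it names no model with the Before score as a covariate.

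The SAP text does not mention percent change. For the Intrinsic Motivation Inventory it plans a t-test of baseline equivalence and a group-by-time interaction. Its Table 5 of planned comparisons is not in the text available, so nothing is inferred from its absence.

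The assumptions are in Protocol Section 3.3. The aim is to "detect a clinically significant difference in the Wolf score changes", at 80% power and a 5% alpha. The remaining inputs read: "With presumed correlation among repeated measures of 0.1 and effect size of 0.3". The stated need is 25 per group, and "Due to possible subject attrition, we will use a total of 30 subjects in each of the two groups".

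**The concern.** A change score subtracts the whole baseline value. When pre and post scores are weakly correlated, that adds more noise than it removes. Percent change also divides by baseline, so subjects with low baselines count for more. Regression on the Before score removes only the part of baseline that predicts the later score, so in large samples its variance is never above that of absolute change.

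Section 3.3 assumes a correlation of only 0.1, where this matters most, and itself calls stroke an extremely variable condition. At stake is precision: a real training effect may be estimated with a needlessly wide interval and missed. Percent change also cannot be set directly against a minimum clinically important difference stated in the outcome's own units.

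**Working it through.** **Inputs from Protocol Section 3.3.** Power 0.80, alpha 0.05, correlation ρ = 0.1, effect size 0.3, 25 per group before the attrition allowance (25/30 implies 16.7% loss). Read as Cohen's f with two groups, 0.3 gives d = 2 × 0.3 = 0.6 SD.

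**Assumed, not in the documents.** The SD, CV and distribution of the WMFT. Baseline CV is varied from 0.15 to 0.5.

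**1. The plan's own figure.** For the between-groups effect in a repeated-measures ANOVA with *m* measurements, λ = f²·N·m / [1 + (m − 1)ρ]. With two groups, m = 2 and N = 50: λ = 0.09 × 50 × 2 / 1.1 = 8.18 on 1 and 48 df, power 0.800. So 25 per group reproduces. This test averages the Before and later scores, so its 80% is not the power for a training effect that appears only after training.

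**2. Variance of each estimate, in units of the outcome variance.**

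- Absolute change: 2(1 − ρ) = 2 × 0.9 = 1.80.
- Adjusted for baseline: 1 − ρ² = 1 − 0.01 = 0.99.

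**3. Power at 25 per arm for a 0.6 SD difference after training.**

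- Pre-post Therapy Type by Test contrast, which is the comparison of absolute change: λ = 0.6² × 12.5 / 1.80 = 2.50 on 1 and 48 df, power 0.34.
- Baseline-adjusted difference: λ = 0.6² × 12.5 / 0.99 = 4.55 on 1 and 47 df, power 0.55.

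**4. Number per arm for 80% power, normal approximation.** n = 2(1.960 + 0.842)² × variance / 0.6².

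- Absolute change: 2 × 7.85 × 1.80 / 0.36 = 78.5, so 79.
- Adjusted: 2 × 7.85 × 0.99 / 0.36 = 43.2, so 44.

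**5. Percent change, by simulation.** Scores were lognormal at both times, with correlation set on the log scale and an additive 0.6 SD effect. There were 25 per arm and 40,000 trials per setting. A t-test on 100 × (post − pre)/pre was compared with ANCOVA on the post score.

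| ρ | CV | Adjusted | Percent change |
|---|---|---|---|
| 0.1 | 0.15 | 54.2% | 32.9% |
| 0.1 | 0.3 | 54.6% | 32.1% |
| 0.1 | 0.5 | 56.2% | 31.1% |
| 0.5 | 0.15 | 66.3% | 54.2% |
| 0.5 | 0.3 | 66.3% | 54.8% |
| 0.5 | 0.5 | 67.0% | 58.0% |
| 0.8 | 0.15 | 92.3% | 90.3% |
| 0.8 | 0.3 | 92.1% | 91.4% |
| 0.8 | 0.5 | 90.8% | 94.4% |

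At ρ = 0.1, 80% power needs about 46 per arm adjusted and 84 to 96 with percent change. Across the two skewed data models tried, the lowest power for percent change at ρ = 0.1 is about 29%. With no true effect, each method rejects in about 5% of trials.

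**6. Where the loss arises.** At ρ = 0.1 the adjusted analysis has about 55%, absolute change about 34-35% and percent change about 29-33%. Most of the drop is already there before anything is divided by baseline.

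**7. Sensitivity to the data model.**

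- ρ = 0.7, 30 per arm, both scores lognormal: percent change against adjusted is 86% against 89% at CV 0.3, and 91% against 89% at CV 0.5.
- ρ = 0.7, 30 per arm, on the simulation described only as having a skewed baseline: 78% against 89% at CV 0.3, and 71% against 88% at CV 0.5.
- ρ = 0.1, 25 per arm, normal scores with baseline floored at 10% of its mean: percent change falls to 21.9% at CV 0.3 and 11.6% at CV 0.5, against 54.4%. Here dividing by baseline adds a large loss of its own.

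**The case against.** The strongest objection is that percent change is not a planned test. The ANOVA is the only formal analysis named. Percent change follows as a way of quantifying effects, with no alpha and no part in the sample size. This stands. A reader might infer that it is a second confirmatory route competing with the ANOVA, but the text does not say so. The ANOVA remains the named test and the published minimum differences the yardstick.

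A reader might also infer that dividing by baseline is the main fault, or that percent change always loses. Neither is supported. Under the skewed models most of the loss at correlation 0.1 comes from not adjusting, and at 0.7-0.8 percent change can draw level or lead. It follows that removing percent change alone would leave the pre-post ANOVA contrast with the same weakness.

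Two further limits stand. If 0.3 is taken as f for the interaction itself, it means a 1.2 SD difference in change, and the two-test interaction has 87% power at 25 per group. The absolute powers then no longer apply, although the variance factors of 1.80 and 0.99 do. And duration of motor activity is recorded during training, with no evident earlier value to adjust for.

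**Conclusion.** The point holds as a minor, inexpensive gain in efficiency. The Protocol names no baseline-adjusted estimate. At its own correlation of 0.1, with d = 0.6 and 25 evaluable per arm, unadjusted change and percent change have about 29-35% power against about 55% adjusted. The adjusted and absolute-change figures follow from Section 3.3 once 0.3 is read as f and the 0.6 SD difference is placed after training. The percent-change figures also need the assumed skew and a CV of 0.3-0.5. If the true correlation is well above 0.1, the gain is smaller and may vanish or reverse against percent change. This is a matter of precision and not of validity, since Type I error stays near 5%. The calculation covers a two-arm, pre-post comparison. It does not cover the full four-test interaction or the month 1 versus month 6 contrast, which does not use the Before score.

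**What to change.** In Protocol Section 5, state that for the WMFT and the other outcomes measured before training, the training effect is the arm difference at each post-training test, adjusted for the Before score, with a 95% interval. Report it in the outcome's own units so that it can be set against the published minimum clinically important difference. State that percent change is relative to the Before score and is descriptive only, without a test. Exclude duration of motor activity from this wording.

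The cost is a sentence or two and a covariate in the model. No new data are needed, because Section 4.2 already schedules clinical and kinematic testing before training and at each later test.

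### Protocol Section 5 names no decisive test of the training effect on the primary WMFT, and the one contrast it singles out (Month 1 versus Month 6) does not measure that effect

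*Protocol*

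**What the plan says.** Protocol Section 5 sets the primary outcomes: "Our primary outcome measures will be the WMFT (Aim 2) and the duration of motor activity (measure of compliance, Aim 1"). These and all secondary outcomes "will be subjected to a repeated measured analysis of variance, with between-group factors Therapy Type" (virtual simulations, standard exercise) and a within-subject factor Test with four levels: Before, Post, one-month retention and six-month retention. Post-hoc work on the interaction is to concentrate on Month 1 against Month 6.

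The section then lists further ways of looking at the effect: "We will be quantifying training effects by comparing group means as well as by percent change in performance, and by comparing the recovery curves" over Tests 1 to 4. It closes by saying that the clinical outcomes have "published minimum clinically important differences which we will use to evaluate the significance of our findings". It gives no MCID value and no rule for applying one.

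The only significance level in the protocol is in Section 3.3, for the sample size: "we will assume a power level of .8 and a significance level of 0.05". That section also says that the study is sized for a clinically significant difference in Wolf score changes. Section 5 contains no alpha, no multiplicity rule and no ranking of the comparisons.

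The SAP pages available name the Intrinsic Motivation Inventory as primary and do not mention the WMFT. The SAP's summary table of planned comparisons (Table 5) is not among them, so nothing is concluded from its absence.

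**The concern.** A primary outcome needs one result, fixed in advance, that decides whether the trial was positive. Section 5 does not give one for the WMFT.

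- **The ANOVA has more than one term.** It has a Therapy Type main effect and a Therapy Type by Test interaction, and neither is named as decisive. The interaction covers all four tests at once, so a significant result would not say when the arms differ or in which direction.
- **The one contrast given prominence compares two retention tests.** It asks whether the arms diverge after training has ended, not whether training worked.
- **The remaining comparisons are unranked.** Group means (at which test?), percent change (over which interval?) and recovery curves (compared how?) can disagree on the same data.
- **The MCID is tied to the word significance.** The section does not say whether it applies to the difference between arms or to each arm's own change.

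A reader of the results could not tell whether the WMFT comparison reported as the training effect was the one intended, and its error rate could not be stated.

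**Working it through.** **1. The plan's own figure.** Section 3.3 gives power 0.80, alpha 0.05 and "With presumed correlation among repeated measures of 0.1 and effect size of 0.3", leading to "we will need a sample size of 25 subjects in each of the three groups (HBVS, ME and MnE"). Reading 0.3 as Cohen's f, the G*Power between-factors formula with k = 2 groups, m = 2 measurements and N = 50 is

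λ = f²·N·m / (1 + (m − 1)ρ) = 0.09 × 50 × 2 / 1.1 = 8.18, on 1 and 48 df, giving power 0.800.

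So 25 per group is reproduced, but as a group main effect over two measurements. The interaction formula, λ = f²·N·m / (1 − ρ), needs 21 per group with two tests or 15 with four (two groups). The sample size therefore does not point to the interaction as the deciding test. Section 3.3 also refers to three groups and then to two ("we will use a total of 30 subjects in each of the two groups"). That is a separate inconsistency and does not affect what follows.

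**2. The Month 1 versus Month 6 contrast.** Let both arms start at mean b, and let the virtual arm gain g by Post and keep it. The other arm stays at b.

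- Before-to-Post change, difference between arms: (b + g − b) − (b − b) = g.
- Month 1 to Month 6 change, difference between arms: [(b + g) − (b + g)] − (b − b) = 0.

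A fully retained benefit of any size gives zero on the only contrast that Section 5 names.

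**3. False-positive rate under different readings.** For j independent tests at 0.05 the rate is 1 − 0.95^j: 5.0%, 9.8%, 14.3%, 18.6% and 22.6% for j = 1 to 5. The comparisons here share data and are correlated, so the rates were simulated.

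- From the protocol: two arms, four tests, 25 or 30 per arm, correlation 0.1.
- Assumed: correlations of 0.5 and 0.8 as alternatives, compound symmetry, normal scores, coefficient of variation (CV) 0.15 to 0.30, each comparison tested at two-sided 0.05, percent change taken from Before to Post, curves compared by linear slope, and an MCID cut of 0.5 SD where a responder test is included.
- No arm effect; 8,000 trials per setting. The Monte Carlo standard error near 15% is √(0.15 × 0.85 / 8000) = 0.4 percentage points.

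For the interaction with 25 per arm, df = (2 − 1)(4 − 1) = 3 and (50 − 2) × 3 = 144.

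| What counts as a test, any one sufficing | False-positive rate |
|---|---|
| Interaction only | about 5% |
| Interaction, percent change | 7.2–8.3% |
| Interaction, Before-to-Post change in means, percent change | 8.1–9.4% |
| The same plus slope over Tests 1–4 | 11.4–12.4% |
| Interaction, Post means, percent change, slope | 13.7–15.5% |
| Four comparisons plus an MCID responder test (group means read as change, Post score or four-test average) | 12.3–18.7% |
| Interaction, both Post means and change, percent change, slope, Month 1 versus Month 6 | about 18–19% (highest single setting 19.7%) |

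The choice of which comparisons are tests moves the answer far more than the correlation or the CV does.

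**The case against.** The strongest reply is that Section 5 names one inferential procedure, the ANOVA with post-hoc work on its interaction. The next sentence speaks of quantifying effects, which can fairly be read as describing their size. On that reading, with one ANOVA term named, the rate is 5%. The routes also overlap: an ANOVA already compares group means, and its interaction already compares the four-test profiles. Treating Post means and a linear slope as extra tests is the analyst's choice, not the protocol's. The 0.05 belongs to the sample-size paragraph and is not assigned to these comparisons.

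Much of this stands. A reader might infer that the plan carries a false-positive rate of about 15% as it is written. The documents do not support that. The figure arises only if four particular tests are run at 0.05 and any one counts as success, and the protocol says neither.

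A reader might also infer that each arm's own mean change will be held against the MCID, so that one arm could pass and the other fail by chance. The protocol states no such rule. Section 3.3 attaches clinical significance to a difference in Wolf score changes, and an MCID required in addition to statistical significance would lower the error rate.

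The reply does not supply the missing decision rule. Even if only the ANOVA is inferential, its deciding term is not named, and the one contrast given prominence leaves out both Before and Post.

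**Conclusion.** The point holds as a gap in specification. Section 5 provides no single error-controlled test of the training effect on the WMFT, and Month 1 versus Month 6 cannot serve as one. This follows from the text and needs no assumption beyond reading Month 1 and Month 6 as the two retention tests.

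The inflation is conditional: about 5% if the interaction alone decides, roughly 7% to 15% if the other comparisons are also tested at 0.05 with any one sufficing, and up to about 19% with an MCID responder test or further contrasts. The ranges rest on the assumed forms of the tests, the correlation (0.1 from the protocol; 0.5 and 0.8 assumed) and the assumed CV. No one figure should be quoted as the plan's error rate.

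The change should be made, because it settles what may be claimed for a primary outcome and requires only wording, best settled before outcome data are examined.

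**What to change.** Amend protocol Section 5 only:

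1. Name one decisive WMFT result: the between-arm difference in change from Before to Post, estimated from the planned four-test model, at two-sided 0.05 with its 95% confidence interval. This agrees with Section 3.3, which speaks of changes in the Wolf score.
2. Reword the Month 1 versus Month 6 sentence so that this contrast is secondary and concerns retention. If it is left as it stands, it will compete with the decisive contrast.
3. Label percent change, group means at single tests and recovery curves as descriptive, with no claim of significance.
4. Use the published MCID only to interpret the size of the between-arm difference and its confidence interval. It should not act as a second standard of significance or be applied to within-arm change.

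The cost is wording. No new data, visits or subjects are needed, and every planned summary can still be reported. The small downside is that a favourable result on a descriptive comparison can no longer be claimed as a positive finding.
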